5.1.1.4.4 Vital Signs

Vital signs will be summarized by treatment group, double-blind treatment/oxybutynin chloride gel sequence, or oxybutynin chloride gel only group, as applicable, and visit for each safety population as follows:

Table 5-19 Vital Signs Summaries

Endpoint	Description	Timing	Methodology
Descriptives	Summary of change from baseline by	Pre-Amendment 3	CFB
	parameter and analysis visit	Weeks 1 to 6; Post-	descriptives
	Parameters specified in Section 6.4.3.1	Amendment 3 Visits	
		B, C, D, E, and F ¹	
Descriptives	Summary of raw values by parameter and	Pre-Amendment 3	Continuous CFB
	analysis visit	all double-blind	descriptives
	Parameters specified in Section 6.4.3.1	visits; Post-	
		Amendment 3 Visits	
		A, B, C, D, E, and	
		F^1	
Descriptives	Summary of raw values and change from	Combined open-	Continuous CFB
	baseline by parameter and analysis visit	label period	descriptives
	Parameters specified in Section 6.4.3.1		

¹ Analysis visits defined in Section 6.2.2.

5.1.1.4.5 Physical Examination

Physical examination assessments will be summarized for each safety population by doubleblind treatment group or oxybutynin chloride gel only group, as applicable, and visit.

Table 5-20 Physical Examination Summaries

Endpoint Description		Timing	Methodology
Each body system at a	Summary of number and percentage of	Visits 8 and F ² ,	Categorical CFB
visit rated	subjects Normal at baseline who shifted to	Combined open-	descriptives
(Normal/Abnormal) ¹	Abnormal post-baseline by parameter and	label period	
	analysis visit	_	

The denominator for calculating the percentages will be based on the number of patients evaluated for a body system at the visit who were rated as Normal for the body system.

5.1.1.4.6 Skin Assessment for Erythema

Skin assessments for erythema will be summarized for each safety population by treatment group and visit for the Pre-Amendment 3 double-blind period and by oxybutynin chloride gel only and visit for the Pre-Amendment 3 open-label period, the Pre-Amendment double-blind and open-label periods combined, and the Post-Amendment 3 open-label period. Additionally, skin assessments for erythema will be summarized by visit for each of the above described.

² Analysis visits defined in Section 6.2.2.

Table 5-21 Skin Assessment for Erythema Summaries

Endpoint	Description	Timing	Methodology
Each erythema	Summary by parameter and analysis visit	Visits C, D, E, and	Categorical CFB
category (none, mild,		F^2	descriptives
moderate, severe) ¹			_

- 1 Participants who have non-missing assessments.
- 2 Analysis visits defined in Section 6.2.2.

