9.7.3 Application Site Erythema Assessment

Skin reactions at the most recently applied gel application site will be assessed for severity of erythema, at each clinic visit *during the treatment period*. Other reactions such as itching, edema, papules, patient-reported erythema, etc. will be recorded as *AEs* using standard medical terminology. The following grading scale will be used to assess skin erythema:

0 = None:	no visible erythema
1 = Mild:	faint or barely perceptible pink color
2 = Moderate:	bright pink or sunburned appearance
3 = Severe:	beet-red appearance

Where there are multiple areas of erythema, the most severe rating should be recorded. Severe reactions (Grade 3) *and* clinically significant problems noted by the patient, investigator, or staff should be recorded as adverse events and will be followed through to resolution.

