11.6.6 Skin Assessments for Erythema

Skin assessments for erythema will be summarized for *each* safety population by treatment group and visit for the *Pre-Amendment 3 double-blind* period and by *oxybutynin chloride gel* only and visit for the *Pre-Amendment 3 open-label* period, *the Pre-Amendment 3 double-blind* and *open-label* periods combined, *and the Post-Amendment 3 open-label period*. Additionally, skin assessments for erythema will be summarized over all visits for each of the above described summaries. Summaries will present the number and percentage of *patients* for each erythema category (none, mild, moderate, and severe). The denominators for calculating the percentages will be based on the number of *patients* with nonmissing assessments.

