5.1.1.4 Safety Analyses

Safety analyses will be based on each safety population.

Baseline assessments for applicable safety endpoints defined as follows:

Table 5-13 Safety Endpoint Baseline Definitions

Parameter	Description	Timing
Clinical laboratory evaluations	eCRF- or (standardized) vendor-provided	Latest non-missing
 Vital signs 	assessments	assessment
 Physical Examination 		on/before treatment
Skin Assessments for		start date
Erythema		

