Appendix 1 Schedule of Events

		Treatment Period						
F. J. C.	Screening Period	Double-Blind Placebo-Controlled					Open-Label Safety	
Evaluation:	Visit 1	Visit 2	Visit 3	Visit 4	Visit 5	Visit 6	Visit 7	Visit 8/ ET
		Week 0	Week 1	Week 2	Week 4	Week 6	Week 8	Week 14
Informed Consent	X							
I/E Criteria	X	X						
Medical History	X	X						
Concomitant Medication	X	X	X	X	X	X	X	X
Physical Examination	X							X
Height and Weight	X							
Vital Signs	X	X	X	X	X	X	X	X
12-Lead ECG	X							
Serum Chemistries	X							X
Hematology	X							X
Urinalysis	X	X^2						X
Urine Culture	X							
Urine pregnancy test ¹	X					X		X
Urodynamics		X				X		
Dispense 2-day Urinary Diary	X		X		X			
Collect 2-day Urinary Diary		X		X		X		
Skin Tolerability Assessment			X	X	X	X	X	X
Adverse Event Assessment			X	X	X	X	X	X
Anticholinergic Questionnaire		X				X		X
Collect PK Sample& Record Date/Time			X	X	X	X		
Dose Titration (if necessary)				X			X	
Randomization		X						
Test Article Dispensing		X		X		X	X	
Test Article Accountability				X		X	X	X

Urine pregnancy test will only be performed for females of childbearing potential.

Note that this table is found in Appendix 1 of OG09002 Protocol Amendment 2, Schedule of Events (Watson Laboratories, Inc. dated 25 June 2012).

A urine sample for on-site urinalysis to determine presence of bacterial infection will be collected.

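### SAP 5.1.1.4.6 drops the protocol's across-visits erythema summary without logging it, and its Table 5-21 conflicts with the plan's own text and schedules on visits and baseline

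*SAP*

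**What the plan says.** Protocol 11.6.6 sets out erythema summaries by visit for four groupings: the Pre-Amendment 3 double-blind period by treatment group, the Pre-Amendment 3 open-label period, those two combined, and the Post-Amendment 3 period. It then adds a further layer: "Additionally, skin assessments for erythema will be summarized over all visits for each of the above described summaries". Results are numbers and percentages of patients per grade, among those with a non-missing assessment.

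SAP 5.1.1.4.6 keeps the same groupings in its opening sentence, including "Skin assessments for erythema will be summarized for each safety population by treatment group and visit for the Pre-Amendment 3 double-blind period". Its second sentence reads: "Additionally, skin assessments for erythema will be summarized by visit for each of the above described".

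Table 5-21, directly below, gives the timing as "Visits C, D, E, and" F. It gives the method as Categorical CFB descriptives (CFB is change from baseline), and footnote 1 restricts the rows to participants with non-missing assessments. Table 5-13 includes erythema among the endpoints whose baseline is the latest value on or before the treatment start date.

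On collection, Protocol 9.7.3 states: "Skin reactions at the most recently applied gel application site will be assessed for severity of erythema". The Post-Amendment 3 schedule (Protocol Appendix 1, SAP 4.3) marks this at Visits C, D, E and F. The Pre-Amendment 3 schedule (SAP Appendix 1) has a row "Skin Tolerability Assessment" marked at Visits 3 to 8.

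**The concern.** Skin tolerability is part of the secondary objective (Protocol 8.2, SAP 4.2), and the graded erythema assessment is the measure that SAP 4.2 assigns to it. Three things in the SAP section do not fit together.

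- The protocol's summary across visits has gone. The sentence that carried it now duplicates the one before it, which suggests a transcription slip rather than a decision. SAP 5.2 says that changes from the protocol are detailed in 5.2.2, but that log has no erythema entry.
- The table's timing cell is narrower than the text above it. A programmer working from the table would produce Post-Amendment 3 output only.
- The method label and the baseline table call for a pre-treatment grade that the study does not schedule.

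The first matters most. A set of by-visit percentages does not show how many children had erythema at any time, because the same or different children may be affected at each visit.

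**Working it through.** The plan states no figure for this point, so there is none to reproduce. The check compares the provisions, counts schedule marks and works one illustration.

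**1. The two sentences.** Protocol: "skin assessments for erythema will be summarized over all visits for each of the above described summaries". SAP: "Additionally, skin assessments for erythema will be summarized by visit for each of the above described". The SAP's preceding sentence already specifies visit for each grouping, so its second sentence adds nothing. The SAP's erythema section and table do not supply the across-visits summary in any other form.

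**2. Visits in Table 5-21 against visits scheduled.**

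| Period | Scheduled erythema/skin assessments | Named in Table 5-21 |
|---|---|---|
| Pre-Amendment 3 double-blind | 4 (Visits 3–6) | 0 |
| Pre-Amendment 3 open-label | 2 (Visits 7–8) | 0 |
| Post-Amendment 3 open-label | 4 (Visits C–F) | 4 |
| Total | 10 | 4 |

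Neighbouring tables do name Pre-Amendment 3 time points: Table 5-19 (vital signs), Table 5-20 (physical examination, Visit 8) and Table 5-22 (anticholinergic questionnaire). Table 5-23 is Post-Amendment 3 only because the vision questionnaire was introduced then. Erythema has no such reason.

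**3. Baseline.** Tables 6-4 and 6-5 place the safety baseline at Visit 1/Visit 2 or Visit A/Visit B, up to Treatment Day 1. Erythema assessments scheduled there number 0 of 2 visits in each part. The activity lists for Visits A and B in Protocol 9.5 contain none either. The protocol grades a site to which gel has been applied, so a pre-dose grade is not defined.

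Table 5-2 does not define Categorical CFB descriptives. The nearest entry, categorical descriptives, sets N1 as participants with a non-missing baseline. On scheduled data that gives N1 = 0. Footnote 1 of Table 5-21 instead uses participants with a non-missing assessment. These are two incompatible denominators.

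**4. What by-visit tables leave open (illustration; the rates are assumptions).** Let a share *p* of children have erythema at each of *k* visits, with everyone assessed every time. The share ever affected is:

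- *p* at minimum, if the same children are affected each time;
- 1 − (1 − *p*)^*k* if visits are independent;
- min(1, *k·p*) at maximum, if different children are affected each time.

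| *p* | *k* | Minimum | Independent | Maximum |
|---|---|---|---|---|
| 5% | 4 | 5% | 1 − 0.95^4 = 18.5% | 20% |
| 10% | 4 | 10% | 1 − 0.90^4 = 34.4% | 40% |
| 20% | 4 | 20% | 1 − 0.80^4 = 59.0% | 80% |
| 10% | 2 | 10% | 1 − 0.90^2 = 19.0% | 20% |

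*k* = 4 fits the Pre-Amendment 3 double-blind and Post-Amendment 3 periods; *k* = 2 fits the Pre-Amendment 3 open-label period. All rows with the same *p* give identical by-visit tables.

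**The case against.** The strongest reply is that little is lost in practice, and several parts of it stand.

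- *A reader might infer that the placebo comparison has been abandoned.* It has not. The text of SAP 5.1.1.4.6 still commits to the double-blind summary by treatment group and visit. The omission is confined to the table's timing cell, so this is a conflict between text and table.
- *A reader might infer that the analysis cannot be run without a baseline.* It can. Table 5-21 describes a summary of each grade by visit, with no shift or change, and footnote 1 supplies a workable denominator. SAP 5.1.1.1.3 lets individual analyses depart from the general definitions. The SAP also uses the CFB label loosely elsewhere: Table 5-19 attaches it to a row of raw values. The label and the Table 5-13 entry are misapplied, but they do not block by-visit counts.
- *A reader might infer that the protocol requires a worst grade per patient.* It asks for a summary over all visits and does not say how a child with different grades at different visits is to be counted. Worst grade is a natural reading, but it is not the protocol's stated rule.
- *Adverse event tables cover part of the gap.* Under Protocol 9.7.3, Grade 3 reactions, clinically significant problems and patient-reported erythema are recorded as adverse events. SAP Table 5-16 counts each participant's most intense occurrence, by treatment group in the double-blind population. That leaves mild and moderate erythema graded by site staff.
- *Sites rotate and only the latest is graded.* A summary across visits would still miss reactions at ungraded sites. That is a limit of data collection, which this change does not cure.
- *Table layouts sit in a separate specification,* which is not available here. It may fill some gaps, but the SAP should not leave it to choose between conflicting instructions.

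One could also try to rescue the baseline by treating Visit 6 as the baseline for Pre-Amendment 3 open-label patients. Table 6-4 does not allow it, because it ties baseline to Visit 1/Visit 2.

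**Conclusion.** The point holds as a should-fix on descriptive safety reporting. A summary planned in the protocol, bearing on a secondary objective, has been dropped without record. The table names 4 of 10 scheduled assessments and contradicts the text on the rest. The erythema baseline has no scheduled assessment behind it in either part.

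The main consequence is limited to the per-patient frequency of mild and moderate erythema across visits. Its size depends on rates that the documents do not give. At an assumed 10% per visit over four visits, between 10% and 40% of children could have been affected at some time (34% if visits were independent), and by-visit tables cannot tell these apart. The documents do not support a claim that the blinded skin data will go unanalysed, or that no erythema output can be produced. No hypothesis test or efficacy conclusion is affected.

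**What to change.** Amend the SAP as follows.

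- **Section 5.1.1.4.6:** reinstate the across-visits summary for every grouping in the text: Pre-Amendment 3 double-blind by gel and placebo, Pre-Amendment 3 open-label, the two combined, and Post-Amendment 3. Define it, for example as each patient's worst post-dose grade in the period. Without a definition, the general rule in Table 5-2 (one count per category) would place a child with mild and later moderate erythema in both rows.
- **Table 5-21:** add Visits 3 to 8 to the timing. Replace Categorical CFB descriptives with counts and percentages over patients with a non-missing assessment, in line with the table's own footnote 1.
- **Table 5-13:** delete the erythema entry ("Skin Assessments for" Erythema).
- **Section 5.2.2:** record these changes.

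The cost is SAP wording and one additional across-visits erythema summary, presented for each grouping. All the data are already collected under the existing schedules.

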5.1.1.5 Other Assessments

5.1.1.5.1 Anticholinergic Questionnaire

Anticholinergic symptom questionnaire data will be summarized for the Pre-Amendment 3 double-blind safety population by treatment group and visit and by treatment group, dose level, and visit for the double-blind period. Anticholinergic symptom questionnaire data will be summarized by oxybutynin chloride gel only and visit and by oxybutynin chloride gel only, dose level, and visit for the Pre-Amendment 3 open-label period and the Pre-Amendment 3 double-blind and open-label periods combined, and for the Post-Amendment 3 open-label period.

Additionally, shifts from baseline for each question will be provided for all evaluable shifts. An evaluable shift is one where both the baseline evaluation and on-treatment evaluations are recorded.

Table 5-22 Anticholinergic Questionnaire Summaries

Endpoint	Endpoint Description		Methodology
Each question on the	Each question on the Categorical summary of number and		Categorical
questionnaire1 overall	percentage of participants in a response	Weeks 0, 6, and 14;	descriptives
and by age group and	category (no, mild, tolerable, or	Post-Amendment 3	
sex	intolerable, applicable) by question and	Visits B, C, D, E,	
	analysis visit; shift tables summarizing	and F ²	
	the shift in categorical response from		
	baseline to each post-baseline visit (for		
	Pre-Amendment 3 and also for Post-		
	Amendment 3)		

- 1 Participants who have non-missing assessments.
- 2 Analysis visits defined in Section 6.2.2.

5.1.1.5.2 Vision Questionnaire

Visit symptom questionnaire data will be summarized for the Post-Amendment 3 Open-Label Safety Population by visit overall and for each dose level.

Table 5-23 Vision Questionnaire Summaries

Endpoint	Description	Timing	Methodology
Each question on the	Summary by question and analysis visit	Post-Amendment 3	Categorical
questionnaire (yes, no) ¹		Visits B, C, D, E,	descriptives
		and F ²	

- 1 Participants who have non-missing assessments.
- 2 Analysis visits defined in Section 6.2.2.

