9.2 Rationale for Study Design and Control Group

Prior to Amendment 3, this study was designed as a double-blind, placebo-controlled study followed by an open-label safety extension, with a total planned enrollment of approximately 96 patients and the expectation that a minimum of 25 evaluable pediatric patients would complete the open-label extension period and provide long-term (14-week) safety data for oxybutynin chloride gel in pediatric patients.

Six weeks of treatment is sufficient

to observe a treatment effect. The additional 8 weeks of open-label treatment *was intended to* increase the number of patient exposures to oxybutynin chloride gel and generate long-term safety data. *Post-Amendment 3 enrollment, the open-label treatment will allow for further ascertainment of efficacy and safety data for oxybutynin chloride gel in pediatric patients.* The use of urinary diaries will generate *data* for assessment of primary and secondary endpoints in this study. *Assessment of* urodynamics is a *customary* and accepted method to measure changes in bladder function with oxybutynin and other anticholinergic agents.^{9,10} The percent*age of* catheterizations without leakage is a clinically meaningful endpoint, and catheterization volume *is an accepted* surrogate measure of changes in bladder capacity.

Safety monitoring for this study, including physical examination, vital signs, clinical laboratory measurements, and skin erythema assessments, are evaluations previously used to evaluate the safety of transdermal oxybutynin in pediatric *patients*. *Post-Amendment 3, vision assessment prior to or at the Baseline Visit was added for patients < 8 years old and a vision symptom questionnaire for all patients was added to monitor visual changes.*

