9.8.6 Vision Symptom Questionnaire

Post-Amendment 3, patients/caregivers will be asked to complete a Vision Symptom Questionnaire at Visits B, C, D, E, and F (Appendix 6). The questionnaire will ask patients/caregivers to describe any visual impairment or eye conditions for the patient.

Adverse events of vision disorders and/or symptoms detected on the Vision Symptom Questionnaire will be reported on the Adverse Event Form. The severity of the event and the relationship to the study drug will be assessed by the investigator and reported on the Adverse Event Form.

If a patient < 8 years old has started treatment and develops visual or ophthalmologic symptoms (ie, blurry vision, dry eye, dilated pupils, constant squinting, eyes drifting outward) it will be recommended that the patient is referred to a pediatric ophthalmologist for a comprehensive eye examination.

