11.7.6 Vision Symptom Questionnaire

Vision symptom questionnaire data will be summarized for the Post-Amendment 3 safety population by visit and by dose level for the open-label period.

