Appendix 5 Anticholinergic Questionnaire

Appendix 6 Vision Symptom Questionnaire for Parent/Caregiver

Visit			
Patient Initials:	Patient #	_	
Place an "X" in the a	ppropriate box as it applies to ye	our child	
Description		(circle Yes or No as indicated)	
Do you suspect anything is wrong with	your child's eye/vision	Yes	No
Has your child ever been diagnosed wi	th an eye condition	Yes	No
Have you observed any problems or ch lashes or the area around the eyes	ange in the whites, pupils, lids,	Yes	No
Has your child shown any signs ofabno dizziness	rmal sensitivity to light or	Yes	No
Has your child had any complaints of n	ausea or headaches	Yes	No
Turning of one eye (in, out, up or down	1}	Ves	No
Poking at the eyes or frequent rubbing		Yes	No
Excessive blinking		Yes	No
Unusual watering or discharge of the e	ye	Yes	No
Poor eye contact		Yes	No
Covering or closing an eye when lookin	ig at an item of interest	Yes	No
Abnormal head posture such as tilting forward or backward when viewing an	the head to one side or moving item of interest	Yes	No
Squinting		Yes	No
Playing the head close to an item of int	aract	Yes	No

Source: Minnesota Department of Health (MDH); Community and Family Health Division; Child and Adolescent Health Unit; Vision Screening Procedures for Infancy, Childhood and School Age Children; June 2014. http://www.health.state.mn.us/divs/cfh/topic/visionscreening/ content/document/pdf/vision_screening_manual.pdf.

Inaccuracy in reaching for an item of interest

If a patient < 8 years old has started treatment and develops visual or ophthalmologic symptoms (ie, blurry vision, dry eye, dilated pupils, constant squinting, eyes drifting outward) it will be recommended that the patient is referred to a pediatric ophthalmologist for a comprehensive eye examination.

Yes

No

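### SAP Table 5-23 summarises the vision symptom questionnaire only as Yes/No counts by visit, so its summary cannot separate a new Yes from one already present at Visit B

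*SAP*

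**What the plan says.** Protocol 9.2 gives the purpose: "a vision symptom questionnaire for all patients was added to monitor visual changes". Protocol 9.8.6 schedules the "Vision Symptom Questionnaire at Visits B, C, D, E, and F". In the Visit B activity list (Protocol 9.5.2.1) the form comes before dispensing and the supervised first application, so Visit B is a pre-treatment record.

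The items in Protocol Appendix 6 are answered Yes or No. Most are undated, for example "Do you suspect anything is wrong with" the child's eye or vision. One is a lifetime question: "Has your child ever been diagnosed" with an eye condition. No recall period is printed.

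Protocol 11.7.6 states the analysis: "Vision symptom questionnaire data will be summarized for the Post-Amendment 3 safety population by visit and by dose level for the open-label period". SAP 5.1.1.5.2 follows it. Table 5-23 gives "Summary by question and analysis visit" at Visits B to F, with categorical descriptives as the method. SAP Table 5-2 defines that method as counts and percentages per category and lists shift analysis as a separate method, which Table 5-23 does not use.

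For the anticholinergic questionnaire, SAP 5.1.1.5.1 adds that "shifts from baseline for each question will be provided for all evaluable shifts", and Table 5-22 includes Post-Amendment 3 in those shifts.

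**The concern.** The instrument was added to detect change, yet its planned summary contains no within-child comparison. Post-Amendment 3 has no comparator, so a child's own Visit B answer is the natural reference for any later Yes.

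Counts by visit lose that link in two ways. A child who becomes Yes can be offset by another who becomes No. The set of children answering also shrinks, so a percentage can move without any child's answer changing.

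At stake is how readable one safety output is. A flat row could be taken as no new symptoms, or a rising row as emerging symptoms, when the table supports neither conclusion.

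**Working it through.** No figure in the documents is in dispute. The check sets the planned methods side by side and then asks what by-visit counts can reveal.

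**Planned methods in the SAP, assessments with a baseline**

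| Assessment | Within-child comparison with baseline |
|---|---|
| Anticholinergic questionnaire (Table 5-22) | Shift to each post-baseline visit |
| Laboratory (Table 5-17) | Change from baseline and shift |
| Vital signs (Table 5-19) | Change from baseline |
| Physical examination (Table 5-20) | Normal to Abnormal |
| Vision questionnaire (Table 5-23) | None |

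**What two by-visit counts allow**

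Let n children answer at both visits, with b Yes at Visit B and w Yes later. The number moving from No to Yes lies between max(0, w − b) and min(w, n − b). Take n = 25, the planned Post-Amendment 3 minimum (Protocol 11.1). The values of b and w, and complete data, are assumptions.

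| b | w | No at Visit B (25 − b) | Newly Yes, lowest | Newly Yes, highest |
|---|---|---|---|---|
| 3 | 3 | 22 | max(0, 0) = 0 | min(3, 22) = 3 |
| 5 | 5 | 20 | max(0, 0) = 0 | min(5, 20) = 5 |
| 5 | 6 | 20 | max(0, 1) = 1 | min(6, 20) = 6 |
| 8 | 8 | 17 | max(0, 0) = 0 | min(8, 17) = 8 |

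In the last row the newly-Yes proportion among children at risk could be 0/17 = 0% or 8/17 = 47%, and the by-visit counts would be identical. The upper end requires every baseline Yes to resolve, so it is a bound and not an expectation.

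**Effect of patients leaving**

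The protocol expects about 10 patients to complete 14 weeks (Synopsis; Protocol 11.1 gives 10 as a minimum). Suppose 8 of 25 are Yes at Visit B (8/25 = 32%), 10 remain at Visit F and no answer changes. The remaining 10 contain between max(0, 10 − 17) = 0 and min(8, 10) = 8 of the Yes children. The Visit F figure could then be anywhere from 0% to 80% with no change in any child. A shift table restricted to children with both answers removes this artefact.

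**The lifetime item**

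If answered consistently, a Yes here cannot revert to No. In a fixed set of children there is no cancellation, and any rise after Visit B equals the new diagnoses among those who were No. Two limits remain: the set of children is not fixed, and a further diagnosis in a child already Yes at Visit B cannot show. A shift table cures the first but not the second.

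**The case against.** The strongest case is that vision findings have their own route. Protocol 9.8.6 sends vision disorders and symptoms found on the form to the Adverse Event Form, and Appendix 8 says detection is tracked through adverse event reporting. SAP 5.1.1.4.2 counts an event as treatment-emergent only if it starts or worsens on or after the first dose, which does separate new from old. Listings of raw data are planned (SAP 5.1.1.1.3). All of this stands, and it limits the point to the questionnaire summary. It does not close the gap. Some judgement remains about which Yes is an adverse event, and listings specify no count of new answers. The anticholinergic questionnaire has the same adverse event route (Protocol 9.8.5) and still receives shift tables.

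It can also be said that the two questionnaires differ. The anticholinergic form is graded and also covers Pre-Amendment 3, so only the Post-Amendment 3 visits coincide, and the SAP matches Protocol 11.7.6 on vision. That is fair: this is not a contradiction between documents. A binary response is no obstacle, though. The SAP already tabulates Normal to Abnormal shifts for physical examination.

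A reader might infer that pre-existing eye problems will be reported as on-treatment findings. The documents do not support this: Table 5-23 includes Visit B and attaches no such label to a Yes. A reader might also infer that Visits B and F describe different children. Patients at Visit F are a subset of those at Visit B.

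**Conclusion.** The point holds as a minor one. Table 5-23 shows the pre-treatment level in aggregate but cannot say how many children acquired a Yes on treatment, and its percentages depend on who is still attending. With 25 children and equal assumed counts of 3, 5 or 8, the number newly Yes is undetermined between 0 and 3, 5 or 8. These figures illustrate the ambiguity; the documents give no expected Yes rates.

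The conclusion does not extend to vision safety as a whole, because the treatment-emergent tables and listings cover part of the question. Nor does it make the form defective. A reader might want a recall period added at Visits C to F, but Visit B would then keep open recall and a Yes could become No through wording alone, which would spoil the comparison being added. A newly-Yes count would still not attribute a symptom to the gel, since there is no comparator.

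**What to change.** In SAP 5.1.1.5.2 and Table 5-23, add for each question:

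- a shift from Visit B to each of Visits C, D, E and F, applying the evaluable-shift rule of SAP 5.1.1.5.1 (baseline and on-treatment answers both recorded);
- the number and percentage newly Yes at any post-baseline visit, among children who answered No at Visit B and have at least one later answer.

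Keep the lifetime item in the shift table. Read only No to Yes as new, and add a note that it cannot show a new diagnosis in a child already Yes at Visit B. Reporting it only as a baseline characteristic would discard new diagnoses. Keep the by-visit counts, and do not alter the Appendix 6 wording.

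The cost is a few lines of SAP text and the added tabulations. No new data are needed, and the shift method is already defined in SAP Table 5-2. SAP 5.1 states that the SAP is approved before database lock, so the change fits there. If lock has passed, the output should be labelled as added afterwards.
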